7.6.5 Adverse Event Assessments

7.6.5.1 Performing Adverse Event Assessments

An AE is defined as any untoward medical occurrence in a patient administered a pharmaceutical product (including investigational drug) during the course of a clinical investigation. An AE can therefore be any unfavorable and unintended sign (including an abnormal laboratory finding), symptom, or disease temporally associated with the use of an investigational product, whether or not considered related to the investigational product.

An elective surgical procedure not associated with a worsening of a known underlying medical condition is not considered an AE, and therefore will not be considered an SAE despite requiring hospitalization. However, complications of the procedure will be considered an AE and may be considered an SAE if hospitalization is prolonged (or any other SAE criteria is met). A hospitalization or prolongation of a hospitalization for reasons other than an AE would not be considered an SAE.

AEs will be found by the patient's spontaneous complaint, patient comment cards, or as a result of nonleading questions, physical examination, vital signs, or laboratory tests. AEs include any occurrences that are new in onset or aggravated in severity or frequency from the baseline condition, or abnormal results of diagnostic procedures, including laboratory test abnormalities. Medical histories that are reported at baseline and worsen will be considered as AEs. Lack of efficacy or fluctuation in influenza symptoms will not constitute an AE in this study.

The investigator or subinvestigator is responsible for assessing AEs. AEs should be fully investigated and recorded in detail including the start date, end date (if outcome is other than recovering, not recovered, or unknown), severity, seriousness with a reason of seriousness, relationship with the study drug, action taken to manage the AE, and outcome of the AE in the eCRF

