7.6.5.7 Serious Adverse Events

7.6.5.7.1 Definition

An SAE is defined by international regulations as an AE occurring at any dose that results in any of the following outcomes:

- Death
- Life-threatening condition

- Hospitalization or prolongation of existing hospitalization
- Persistent or significant disability/incapacity
- Congenital anomaly/birth defect
- Other medically important condition

Important medical events that may not result in death, be life-threatening, or require hospitalization may be considered an SAE when, based upon appropriate medical judgment, they may jeopardize the patient and may require medical intervention to prevent 1 of the outcomes listed in this definition. Examples of such medical events include allergic bronchospasm requiring intensive treatment in an emergency room or at home, blood dyscrasias or convulsions that do not result in inpatient hospitalization, or the development of drug dependency or drug abuse. The investigator or subinvestigator will determine the seriousness of all AEs. Test results that meet the following criterion are considered an SAE:

AST or ALT > 3 × upper limit of normal (ULN) and total bilirubin > 2 × ULN

Hospitalization for preplanned procedures or for elective procedures to treat a preexisting condition that did not worsen after study start will not be considered AEs or SAEs. The exception is when the patient experiences another event or has an outcome that is fatal, is life-threatening, leads to prolonged hospitalization, or is considered to be medically significant during/following the procedure. Where applicable, the diagnosis should be reported as the AE instead of the individual symptoms and signs.

[figure not shown]

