7.8.1 Clinical Progression or Lack of Response

In cases where on clinical review, patients appear to be deteriorating clinically or have not responded to the study drug, the investigator should consider the possibility of secondary infections, decompensation of underlying conditions, or progression of influenza. Patients should be assessed, and investigations should be performed as clinically indicated.

In the event an investigator considers that the influenza has not responded and wishes to treat with open-label, commercially-available influenza antivirals (not provided by the sponsor), the patient should stop all blinded study drugs. Since unblinding of the study drugs would not alter the management of the patients, unblinding in this situation is discouraged, and the patients should remain in the study for follow-up as described in Section 7.8. Such cases should be discussed urgently with the sponsor or sponsor's designated Medical Monitors.

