8) Time to improvement in the 3 respiratory symptoms (cough, nasal congestion, and sore throat)

Defined as the time between the initiation of the study treatment and the improvement in the 3 respiratory symptoms. The assessment follows the criteria for the primary endpoint.

9) Time to resolution of fever

Defined as the time between the initiation of the study treatment and the resolution of fever. The resolution of fever is defined as the time when the patient's self-measured temperature becomes $< 37^{\circ}$ C and is maintained at $< 37^{\circ}$ C for a duration of at least 12 hours.

10) Proportion of patients reporting normal temperature at each time point

Defined as the percentage of patients whose temperature resolves to $< 37^{\circ}$ C after the initiation of the study treatment in the analysis population.

11) Body temperature at each time point

Defined as measured axillary temperature.

12) Time to improvement of each influenza symptom

Defined as the time between the initiation of the study treatment and the alleviation of each influenza symptom. The alleviation of a symptom is defined as the time when the symptom is assessed as 0 (None) or 1 (Mild), for a duration of at least 21.5 hours (24 hours -10%).

13) Time to return to preinfluenza health status

Patients will be asked to record their preinfluenza health status between 0 (worst possible health) and 10 (normal health [for someone your age and your health condition]). Return to preinfluenza health status is defined as time from the initiation of the study treatment to time to the same number on scale for preinfluenza health status.

14) Requirement for systemic antibiotics for infections secondary to influenza infection

Defined as the percentage of patients treated with systemic antibiotics.

15) Incidence of influenza-related complications (hospitalization, death, sinusitis, bronchitis, otitis media, and radiologically confirmed pneumonia)

Defined as the percentage of patients in the analysis population who experience each influenza-related complication (hospitalization, death, sinusitis, otitis media, bronchitis, and radiologically-confirmed pneumonia) as an adverse event after the initiation of the study treatment. A specific complication eCRF with diagnostic criteria for the complications of sinusitis, otitis media, bronchitis, and pneumonia will be provided.

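### Section 7.6.5.1 can be read to keep an admission for worsening influenza out of AE and SAE reporting, and secondary endpoint 15 counts admissions only as AEs, so capture may differ between sites

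*Protocol*

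**What the plan says.** Section 7.6.5.1 sets the general scope of adverse events: "AEs include any occurrences that are new in onset or aggravated in severity or frequency from the baseline condition". Later in the same paragraph comes a study-specific exemption: "Lack of efficacy or fluctuation in influenza symptoms will not constitute an AE in this study". The paragraph before it, which deals with elective surgery, ends: "A hospitalization or prolongation of a hospitalization for reasons other than an AE would not be considered an SAE".

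Section 7.6.5.7.1 makes seriousness a property of an AE: "An SAE is defined by international regulations as an AE occurring at any dose that results in any of the following outcomes".

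In Section 9.10.2, item 15 is the percentage of patients "who experience each influenza-related complication (hospitalization, death, sinusitis, otitis media, bronchitis, and radiologically-confirmed pneumonia) as an adverse event" after the start of study treatment. It adds: "A specific complication eCRF with diagnostic criteria for the complications of sinusitis, otitis media, bronchitis, and pneumonia will be provided". The complication checks in Section 7.6.1 and Appendix 1 name the same four diagnoses. Section 9.10.3.2 compares item 15 between S-033188 and each control by Fisher's exact test.

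Section 7.8.1 covers patients who deteriorate or do not respond. It says that "the investigator should consider the possibility of secondary infections, decompensation of underlying conditions, or progression of influenza", but not whether progression is recorded as an AE.

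**The concern.** The trial enrols patients because they are at risk of influenza complications and gives one third of them placebo. An admission caused by the influenza itself is an outcome that item 15 appears meant to capture. If an investigator regards it as lack of efficacy, the exemption removes it from the AE record. Item 15 and SAE reporting both start from that record, so both lose it.

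Two things are at stake. One is complete and even ascertainment of a formally tested secondary endpoint: sites that read the exemption broadly would record fewer admissions than sites that read it narrowly. The other is safety reporting, because the 24-hour duty in Section 7.6.5.7.2 applies to SAEs only. Events not recorded during the trial may not be recoverable afterwards, so a later analysis plan could not reliably repair the loss.

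**Working it through.** The point concerns definitions. The protocol states no admission rate, death rate or power for item 15, so there is no figure to reproduce.

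**Tracing one case.** Take a patient whose influenza worsens until admission, with no pneumonia, other secondary infection or decompensated comorbidity.

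1. *Is it an AE?* Under the exemption in 7.6.5.1, no, if the investigator sees lack of efficacy or fluctuation. Under the aggravation wording in the same paragraph, yes. The text does not say which prevails.
2. *Is it an SAE?* Section 7.6.5.7.1 requires an AE first, so the answer follows step 1.
3. *Is it in item 15?* The definition requires an adverse event, so again the answer follows step 1.
4. *Is there another stated route into item 15?* The complication eCRF, the visit observation and the schedule name sinusitis, bronchitis, otitis media and pneumonia. Hospitalization and death are not listed. Section 7.8.1 asks for urgent discussion with the sponsor when open-label antivirals are considered, but this feeds neither the endpoint nor SAE reporting.

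All routes therefore hang on step 1, where the protocol supports two answers.

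**Scale, under assumed rates.** The only input from the protocol is 395 infected patients per arm (Section 9.2). The admission rates and shares are assumptions.

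- Placebo admissions at 1% to 3%: 395 × 0.01 = 3.95 and 395 × 0.03 = 11.85, so about 4 to 12.
- Of these, 30% to 70% for influenza alone: 3.95 × 0.3 = 1.2 and 11.85 × 0.7 = 8.3, so about 1 to 8 at risk of not being counted.

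**Effect on the test, under assumed rates.** Take a placebo rate p, halved on S-033188, with n = 395 per arm. Power is the sum of the products of the two binomial probabilities over all pairs of counts for which Fisher's exact p-value is at most 0.05 (two-sided). The last two columns assume that half of the admissions go unrecorded in both arms.

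| p | Placebo events, all counted | Power | Placebo events, half unrecorded | Power |
|---|---|---|---|---|
| 1% | 4.0 | 4% | 2.0 | 1% |
| 3% | 11.8 | 22% | 5.9 | 9% |
| 5% | 19.8 | 39% | 9.9 | 18% |

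Power is low even with full capture. In this illustration an equal proportional loss roughly halves it, or worse, while the ratio of rates stays the same.

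**The case against.** The strongest reply is that the protocol never says an admission for influenza is not an AE. The exemption names lack of efficacy and symptom fluctuation. It does not name progression or admission, and illness that worsens until admission fits the aggravation wording at least as well. Section 7.8.1 distinguishes deteriorating patients from non-responders. The sentence on hospitalization without an AE closes a paragraph on elective surgery and probably concerns elective admissions. Item 15 lists hospitalization and death as complications recorded as AEs, which presupposes that investigators report them. Their absence from the complication eCRF proves little, since that form is described as carrying diagnostic criteria, which an admission does not need.

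Most of this stands, and it rules out saying that such admissions are excluded. It does not close the gap. The exemption comes after the general rule, is specific to this study and has no severity limit. Section 7.8.1 handles progression and non-response under one heading, so an investigator can reasonably file one as the other. That item 15 evidently wants these events counted is a reason to make the AE rule deliver them.

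Three stronger inferences are tempting and unsupported:

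- *That the main high-risk outcome is dropped.* Admissions with pneumonia, another secondary infection or a worsened underlying condition remain countable; worsened medical history is expressly an AE. Item 15 is one of 15 secondary endpoints in Section 9.10.2, is not labelled key, and lies outside the stated hierarchy and the sample size calculation.
- *That deaths are lost.* Section 7.6.5.1 does not mention death, and Section 9.11.1 counts deaths separately. Extending the exemption to death is inference.
- *That the comparison is biased toward no difference because placebo loses most events.* This assumes a treatment effect on admissions and a pattern of missed events by arm. The protocol gives neither, and Section 3.2.2 cites trial data in which oseltamivir did not affect hospitalizations.

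Exclusion criterion 1, on influenza needing inpatient care, concerns status at entry and says nothing about admissions during the study.

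**Conclusion.** The concern holds in a limited form. Sections 7.6.5.1, 7.6.5.7.1 and 9.10.2 do not settle whether an admission attributed purely to worsening influenza is an AE, and both SAE reporting and the hospitalization component of item 15 depend on the answer. The supportable consequence is possible loss and uneven ascertainment between sites.

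The size cannot be derived from the protocol. The range of about 1 to 8 uncounted placebo admissions and the fall in power from 22% to 9% at a 3% placebo rate both rest on assumed rates. The conclusion rests on the wording and does not need them. The primary endpoint is unaffected. This should be fixed because the correction is specific and cheap, but it does not put the trial's main conclusion at risk.

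**What to change.** Reconcile the three sections by amendment.

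- **Section 7.6.5.1, with a cross-reference in 7.6.5.7.1:** state that the exemption for lack of efficacy or symptom fluctuation does not apply when the event meets an SAE criterion, in which case it is reported as an SAE.
- **Section 9.10.2, item 15:** define the hospitalization and death components as any influenza-related hospitalization or death after the first dose, regardless of AE classification.
- **Complication eCRF:** add hospitalization and death as two fields on the existing form, so that capture does not depend on the AE decision.

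The cost is a sentence in each of two sections, a cross-reference and two fields. The downside is a few more SAE reports that reflect the disease and not the drug.

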7.6.5.2 Timing

AEs will be collected from the time of informed consent through Visit 7 (Day 22). If a patient withdraws early from the study, the investigator or subinvestigator will make an effort to collect AEs for 21 days after the last dose of the study drug. All AEs will be followed until resolution, stabilization, the condition becomes chronic, or 35 days after the last study drug administration. Serious treatment-related AEs or AEs related to

abnormal liver function tests shown in Appendix 5 will be followed until resolution, stabilization, the condition becomes chronic, or the patient becomes lost to follow-up.

7.6.5.3 Severity

The severity of an event will be categorized by the investigator or subinvestigator according to the following definitions:

- **Grade 1:** mild; asymptomatic or mild symptoms; clinical or diagnostic observations only; intervention not indicated
- **Grade 2:** moderate; minimal, local, or noninvasive intervention indicated; limiting age-appropriate instrumental Activities of Daily Living (ADL)*
- **Grade 3:** severe or medically significant but not immediately life-threatening; hospitalization or prolongation of hospitalization indicated; disabling; limiting self-care ADL**
- Grade 4: life-threatening consequences; urgent intervention indicated
- **Grade 5:** death related to AE
- Instrumental ADLs refer to preparing meals, shopping for groceries or clothes, using the telephone, managing money, etc.
- ** Self-care ADLs refer to bathing, dressing and undressing, feeding self, using the toilet, taking medications, and not bedridden.

Severity assessment will be based upon The Common Terminology Criteria for Adverse Events (CTCAE, Version 4), and can be found at:

http://evs.nci.nih.gov/ftp1/CTCAE/CTCAE_4.03_2010-06-14_QuickReference_8.5x11.pdf

The highest severity during the period in which the AE occurred will be recorded in the eCRF.

7.6.5.4 Relationship

The relationship of an event to the study drug will be determined by the investigator or subinvestigator according to the following criteria:

- Related: An AE that can be reasonably explained as having been caused by the study drug. For example, a similar event has been reported previously, or increase/decrease of the dose affects the occurrence or seriousness of the AE, etc.
- Not related: An AE that cannot be reasonably explained as having been caused by the study drug.

7.6.5.5 Expectedness

An AE is expected if it is listed in Expected Adverse Reactions:

- S-033188: In Section "Undesirable Effects" of "SUMMARY OF DATA AND GUIDANCE FOR INVESTIGATORS" in the current Investigator's Brochure (IB) for S-033188.
- Oseltamivir phosphate (Tamiflu[®]): The current version of the Prescribing Information in the US for oseltamivir phosphate capsules in accordance with its approved license/marketing authorization.

7.6.5.6 Adverse Event Assessment of Clinical Laboratory and Other Safety Parameters

For laboratory test results (hematology, blood chemistry, or urinalysis) that worsen from baseline or other abnormal safety assessments (eg, physical examinations, vital sign measurements, ECGs), the investigator or subinvestigator will consider whether these results are clinically significant. Abnormal laboratory test results are defined as values outside the reference range. For test results that are abnormal at baseline and significantly worsen following the initiation of the study, the investigator or subinvestigator must also consider whether these results are clinically significant by the investigator or subinvestigator are to be recorded as AEs. If an abnormal laboratory finding is associated with disease or organ toxicity, the investigator should report only the disease or organ toxicity as an AE.

The investigator or subinvestigator will consider test results to be clinically significant in the following circumstances:

- Test result leads to any of the outcomes included in the definition of an SAE (see Section 7.6.5.7.1)
- Test result leads to a change in study drug dosing or discontinuation from the study
- Test result leads to a concomitant drug treatment or other therapy
- Test result requires additional diagnostic testing or other medical intervention
- Test result meets the management and discontinuation criteria for abnormal liver function tests identified in Section 7.6.5.8

In addition, when any test result meets the management and discontinuation criteria for liver function abnormalities (Section 7.6.5.8), the results of further assessments and required follow-up should be recorded in the Liver Event Form.

7.6.5.7 Serious Adverse Events

7.6.5.7.1 Definition

An SAE is defined by international regulations as an AE occurring at any dose that results in any of the following outcomes:

- Death
- Life-threatening condition

- Hospitalization or prolongation of existing hospitalization
- Persistent or significant disability/incapacity
- Congenital anomaly/birth defect
- Other medically important condition

Important medical events that may not result in death, be life-threatening, or require hospitalization may be considered an SAE when, based upon appropriate medical judgment, they may jeopardize the patient and may require medical intervention to prevent 1 of the outcomes listed in this definition. Examples of such medical events include allergic bronchospasm requiring intensive treatment in an emergency room or at home, blood dyscrasias or convulsions that do not result in inpatient hospitalization, or the development of drug dependency or drug abuse. The investigator or subinvestigator will determine the seriousness of all AEs. Test results that meet the following criterion are considered an SAE:

AST or ALT > 3 × upper limit of normal (ULN) and total bilirubin > 2 × ULN

Hospitalization for preplanned procedures or for elective procedures to treat a preexisting condition that did not worsen after study start will not be considered AEs or SAEs. The exception is when the patient experiences another event or has an outcome that is fatal, is life-threatening, leads to prolonged hospitalization, or is considered to be medically significant during/following the procedure. Where applicable, the diagnosis should be reported as the AE instead of the individual symptoms and signs.

[figure not shown]
7.6.5.7.2 Reporting Serious Adverse Events

All information regarding SAEs, including the SAE itself, associated medications, and SAE narratives, must be entered into EDC within 24 hours from the point in time when the investigator first becomes aware of the SAE. If EDC becomes unavailable, all SAEs must be reported to the CRO or sponsor in detail utilizing the SAE form. Upon availability of EDC, this information must then be entered into EDC. All SAEs must be reported regardless of causal relationship to the study drug. A sample of the SAE form can be found in the Site Regulatory Binder. Follow-up information on the SAE may be requested by the sponsor.

When reporting SAEs, the investigator should record the diagnosis whenever possible. If no diagnosis is available at the time of reporting, individual signs and symptoms can be reported.

In the event of any SAE reported or observed during the study, whether or not attributable to the study drug, site personnel must report the SAE via EDC or if EDC is unavailable, prepare an SAE Form and fax or e-mail the completed form within 24 hours to:

CRO SAE hotline – North America: Telephone:PPO

If follow-up is required or requested, the investigator should enter the new information into EDC. Discharge summaries, medical reports from other departments or other hospitals, autopsy reports, or other relevant documents must be evaluated by the investigator and all relevant information must be included in the follow-up SAE report. Copies of these reports may also be requested by the sponsor.

Appropriate remedial measures should be taken by the investigator using his/her best medical judgment to treat the SAE. These measures and the patient's response to these measures should be recorded. Clinical, laboratory, and diagnostic measures should be employed by the investigator as needed to adequately determine the etiology of the event.

Any SAEs occurring after the AE assessment period specified in Section 7.6.5.2 that is considered to be related to study drug by the investigator must be reported to the sponsor.

The investigator will be responsible for reporting all SAEs to the IRB or IEC through the head of the medical institution in accordance with the local regulatory requirement. The sponsor or its designee will be responsible for reporting SAEs to the regulatory authorities as required by the applicable regulatory requirements.

